10.5 Other Required Reporting

- 10.51 Adverse events to be graded at each evaluation and pretreatment symptoms/conditions to be evaluated at baseline per the CTCAE v4.0 grading unless otherwise stated in the table below:

System Organ Class (SOC)	Adverse event/Symptoms	Baseline	Each evaluation	Non CTCAE Grading Scale (major bleeding scale based on ISTH) See appendix IV
Vascular disorder	Other, specify: Bleeding	X	X	X
General disorders and administration site conditions	Injection site reaction		X	
Investigations	Decreased platelet count	X	X	

- 10.52 Submit via appropriate Academic and Community Cancer Research United (ACCRU) Case Report Forms (i.e., paper or electronic, as applicable) the following AEs experienced by a patient and not specified in Section 10.5:

10.521 Grade 2 AEs deemed *possibly, probably, or definitely* related to the study treatment or procedure.

10.522 Grade 3 and 4 AEs regardless of attribution to the study treatment or procedure.

10.523 Grade 5 AEs (Deaths)

10.5231 Any death within 30 days of the patient's last study treatment or procedure regardless of attribution to the study treatment or procedure.

10.5232 Any death more than 30 days after the patient's last study treatment or procedure that is felt to be at least possibly treatment related must also be submitted as a Grade 5 AE, with a CTCAE type and attribution assigned.

10.55 Refer to the instructions in the Forms Packet (or electronic data entry screens, as applicable) regarding the submission of late occurring AEs following completion of the Active Monitoring Phase (i.e., compliance with Test Schedule in Section 4.0).

10.56 Research Coordinating Center will reconcile the clinical database SAE cases received from ACCRU Sites with the SAE cases that have been transmitted to BMS Global Pharmacovigilance (GPV&E). Frequency of reconciliation will occur no more frequently than quarterly for a maximum of twelve (12) reconciliations and will occur no less than once prior to study database lock. BMS GPV&E will e-mail upon request from the investigator, the GPV&E reconciliation report. Requests for reconciliation should be sent to [name]. The data elements listed on the GPV&E reconciliation report will be used for case identification purposes. If the investigator determines a case was not transmitted to BMS GPV&E, the case will be sent immediately.

11.0 Treatment Evaluation Using RECIST Guideline – Not Applicable

12.0 Descriptive Factors – Not Applicable

13.0 Treatment/Follow-up Decision at Evaluation of Patient

13.1 A patient is deemed *ineligible* if after registration, it is determined that at the time of registration, the patient did not satisfy each and every eligibility criteria for study entry. The patient may continue treatment off-protocol at the discretion of the physician as long as there are no safety concerns, and the patient was properly registered. The patient will go off study.

- If the patient received treatment, all data up until the point of confirmation of ineligibility must be submitted.
- If the patient never received treatment, on-study material must be submitted.

13.2 A patient is deemed a *major violation*, if protocol requirements regarding treatment in cycle 1 of the initial therapy are severely violated that evaluability for primary end point is questionable. All data up until the point of confirmation of a major violation must be submitted. The patient will go off study. The patient may continue treatment off-protocol at the discretion of the physician as long as there are no safety concerns, and the patient was properly registered.

- 13.3 A patient is deemed a *cancel* if he/she is removed from the study for any reason before any study treatment is given. On-study material and the End of Active Treatment/Cancel Notification Form must be submitted. No further data submission is necessary.

14.0 Body Fluid Biospecimens – Not applicable

15.0 Drug Information

15.1 Apixaban (Eliquis®) IND Exempt

- Package Insert is available on the ACCRU web site.

15.11 Background: Apixaban (Eliquis) is an oral direct factor Xa inhibitor which impairs coagulation by inhibiting the conversion of prothrombin to thrombin. It does not require antithrombin for antithrombotic activity and inhibits both free and clot-bound FXa. Apixaban has a half-life of about 12 hours and thus is dosed twice-daily. Bioavailability is approximately 50% after oral dosing with maximum concentrations at 4 hours post ingestion. The pharmacokinetics are linear and plasma protein binding in humans is high at nearly 87% with a volume of distribution of approximately 21 liters. Apixaban is metabolized in the liver mainly via the CYP3A4 pathway. Renal excretion accounts for about 27% of total clearance. Approximately 25% of the drug is eliminated in the urine and feces.

15.12 Formulation: Apixaban (Eliquis®) tablets are available for oral administration in strengths of 2.5 mg and 5 mg of apixaban with the following inactive ingredients: anhydrous lactose, microcrystalline cellulose, croscarmellose sodium, sodium lauryl sulfate, and magnesium stearate. The film coating contains lactose monohydrate, hypromellose, titanium dioxide, triacetin, and yellow iron oxide (2.5 mg tablets) or red iron oxide (5 mg tablets).

15.13 Preparation and storage: Store at room temperature 20°C to 25°C (68°F-77°F); excursions permitted between 15°C and 30°C (59°F-86°F). Please see package insert.

15.14 Administration: Apixaban will be provided in bottles containing 74 tablets of 5 mg for the first 30 days of treatment (28 tablets for days 1-7; 46 tablets for days 8-30). For subsequent months, patients will receive 74 tablets of 5 mg strength.

Administer without regards to meals. If patient is unable to swallow tablets whole, 2.5 or 5 mg tablets may be crushed and suspended in 60 mL of dextrose 5% in water followed by immediate delivery through a nasogastric tube. Apixaban tablets may also be crushed and suspended in water, or 5% dextrose in water (D5W), or apple juice or mixed with apple puree and immediately administered orally. Crushed apixaban tablets are stable in water, D5W, apple juice, and apple puree for up to 4 hours.

15.15 Appearance: Yellow, round, biconvex, film-coated tablets with “893” debossed on one side and “5” on the other side.

15.16 Pharmacokinetic information:

- a) Absorption – Time to peak after oral administration is 3 to 4 hours; bioavailability is approximately 50% for doses up to 10 mg.

- b) Distribution – Plasma protein binding in humans is approximately 87%. The steady-state volume of distribution is approximately 21 L.
 - c) Metabolism – Approximately 25% of an orally administered apixaban dose is recovered in urine and feces as metabolites. Apixaban is metabolized mainly via CYP3A4 and to a lesser extent via CYP1A2, 2C8, 2C9, 2C19, and 2J2
 - d) Excretion Apixaban is eliminated in both urine and feces. Renal excretion accounts for about 27% of total clearance.
 - e) Half-life Elimination – approximately 12 hours
- 15.17 Drug interactions: Apixaban is a substrate of both CYP3A4 and P-gp. Inhibitors of CYP3A4 and P-gp increase exposure to apixaban and increase the risk of bleeding. Inducers of CYP3A4 and P-gp decrease exposure to apixaban and increase the risk of stroke

Strong Dual Inhibitors of CYP3 A4 and P-gp

The dose of ELIQUIS should be decreased to 2.5 mg twice daily when is coadministered with drugs that are strong dual inhibitors of CYP3A4 and P-gp. (e.g.; ketoconazole, itraconazole, ritonavir, or clarithromycin).

In patients already taking ELIQUIS at a dose of 2.5 mg twice daily, avoid coadministration with strong dual inhibitors of both CYP3A4 and P-gp.

Strong Dual Inducers of CYP3A4 and P-gp

Avoid concomitant use of ELIQUIS with strong dual inducers of CYP3A4 and P-gp (e.g. e.g., rifampin, carbamazepine, phenytoin, St. John's wort) because such drugs will decrease exposure to apixaban.

Coadministration of antiplatelet agents, fibrinolytics, heparin, aspirin, and chronic NSAID use increases the risk of bleeding.

Please consult current drug reference sources for a complete list of potential drug interactions.

- 15.18 Please consult the package insert for the most current and complete adverse event information.
- 15.19a Drug procurement: Bristol Myers-Squibb will supply the drug to Biologics, Inc. Each participating ACCRU treating location will order the drug from Biologics, Inc. Fax the Drug Order Request Form (found in the forms packet) to:
- Biologics, Inc.
 - Attn. Clinical Research Services
 - Fax: [REDACTED]

Each participating ACCRU treating location will be responsible for monitoring the supply of apixaban and will use the Drug Order Request Form to order additional supplies as needed.

Outdated or remaining drug is to be destroyed on-site as per procedures in place at each institution.

15.19b Nursing guidelines

- Assess patient's concomitant medications including OTC, and herbal products. There are several drug to drug interactions that may interfere with the absorption of agent. Additionally, warn patient to avoid taking medication with any other anti-platelet agents (i.e. aspirin, NSAIDS, etc.)
- Warn patients of risk of bleeding, (including serious life- threatening internal bleeding). Instruct patients to report these to the study team
- Patients should discuss any procedures with the study team and/or any provider prior to proceeding, due to the risk of post procedure bleeding.
- Rarely patients may have nausea, treat symptomatically and monitor for effectiveness
- Rarely LFT's may be elevated. Follow any monitoring as recommended by the study protocol.

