- 9.1 Concomitant use of strong CYP3A4 inhibitors (e.g., HIV protease inhibitors, systemic ketoconazole (appendix II) should be discouraged. In the case of clinical necessity, for

those patients randomized to apixaban, the dose of apixaban will be reduced to 2.5 mg twice daily while the CYP3A4 inhibitor is given.

- 9.2 Non-steroid anti-inflammatory drugs (NSAIDs) and antiplatelet agents (aspirin) are discouraged but not prohibited. If aspirin use is required, then the dose should be ≤ 100 mg daily. The use of these drugs should be recorded on the CRF.
- 9.3 **Note:** Antiplatelet therapy with a thienopyridine (clopidogrel, prasugrel, or ticagrelor) is an exclusion criterion and not allowed while on protocol therapy.

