- 15.24 **Administration:** Dalteparin will be given 200 IU/kg/day subcutaneously. The dosage will be calculated on the patient's current weight in kilograms, rounded to the nearest whole kilogram. The syringe dose will be chosen based on the weight adjusted calculation (see table 7.11). . The patient will be taught by on site nursing staff how to "waste" from each syringe such that the appropriate weight adjusted dose is delivered. After the first month, dalteparin will be given 150 IU/kg/day subcutaneously. Dalteparin will be dispensed in one month supply aliquots to the patient. Dalteparin will be stored according to the package insert. Patient instructions on proper subcutaneous injection techniques are included in appendix IX.
- 15.25 **Appearance:** Colorless solution in single-dose, prefilled syringes preassembled with a needle guard device. Each syringe contains 2,500, 5,000, 7,500, 10,000, 12,500, 15,000 or 18,000 anti-Factor Xa international units (IU).
- 15.26 **Pharmacokinetic information:**
- a) Onset of action - Anti-Xa activity: Within 1-2 hours
 - b) Duration - >12 hours
 - c) Distribution - Vd: 40-60 mL/kg
 - d) Protein binding - Low affinity for plasma proteins
 - e) Bioavailability - SubQ: 81% to 93%
 - f) Half-life elimination (route dependent) - Anti-Xa activity: 2-5 hours; prolonged in chronic renal insufficiency: 3.7-7.7 hours (following a single 5000 unit dose)
 - g) Time to peak, serum - Anti-Xa activity: ~4 hours
 - h) Excretion - Primarily renal
- 15.27 **Potential drug interactions:** Dalteparin should be used with care in patients receiving oral anticoagulants, platelet inhibitors, and thrombolytic agents because of increased risk of bleeding.
- Please consult current drug reference sources for a complete list of potential drug interactions.
- 15.28 **Known potential toxicities:** As with all anticoagulants, bleeding is the major adverse effect of dalteparin. Hemorrhage may occur at virtually any site. Risk is dependent on multiple variables. Please consult the package insert for the most current and complete information.

Adverse effects by frequency:

>10%:

Hematologic & oncologic: Hemorrhage (3% to 14%), thrombocytopenia (including heparin-induced thrombocytopenia, <1%; cancer clinical

trials: ~11%)

1% to 10%:

Hematologic & oncologic: Major hemorrhage ($\leq 6\%$), wound hematoma (3%)

Hepatic: Increased serum ALT ($>3 \times \text{ULN}$: 4% to 10%), increased serum AST ($>3 \times \text{ULN}$: 5% to 9%)

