Local: Pain at injection site ($\leq 12\%$), hematoma at injection site ($\leq 7\%$)

$<1\%$ (Limited to important or life-threatening):

Alopecia, anaphylactoid reaction, gastrointestinal hemorrhage, hemoptysis, hypersensitivity reaction (fever, pruritus, rash, injections site reaction, bullous eruption), postoperative wound bleeding, skin necrosis, subdural hematoma, thrombosis (associated with heparin-induced thrombocytopenia). Spinal or epidural hematomas can occur following neuraxial anesthesia or spinal puncture, resulting in paralysis.

- 15.29a **Drug procurement:** Pfizer will supply the drug to Biologics, Inc. Each participating ACCRU treating location will order the drug from Biologics, Inc. Fax the Drug Order Request Form (found in the forms packet) to:
Biologics, Inc.
Attn. Clinical Research Services
Fax: [REDACTED]

Each participating ACCRU treating location will be responsible for monitoring the supply of dalteparin and will use the Drug Order Request Form to order additional supplies as needed.

Outdated or remaining drug is to be destroyed on-site as per procedures in place at each institution.

15.29b Nursing guidelines:

- Instruct patients on self-injection technique.
- Warn patient of increased risk of bleeding, including life threatening hemorrhage. Patients should report excessive bruising and/or bleeding to the study team.
- Monitor LFT's and alert study team to changes in values.
- Instruct patients that they need to notify their provider prior to any procedures, as their risk for bleeding is significantly increased.

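### Only the apixaban nursing guidelines have nurses steer patients away from aspirin and NSAIDs: a small, avoidable difference between arms in an open-label bleeding trial

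*Combined protocol and SAP*

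**What the plan says.** The rule on these drugs is in Section 9.2 and is not arm-specific: "Non-steroid anti-inflammatory drugs (NSAIDs) and antiplatelet agents (aspirin) are discouraged but not prohibited". Aspirin, where it is needed, is limited to 100 mg daily, and "The use of these drugs should be recorded on the CRF". Section 9.2 does not say who counsels the patient.

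The nursing guidelines are written separately for each drug.

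- **Apixaban (15.19b).** Nurses review concomitant medication, including over-the-counter and herbal products, and "warn patient to avoid taking medication with any other anti-platelet agents (i.e. aspirin, NSAIDS, etc". They also warn about bleeding and ask patients to discuss procedures with the study team.
- **Dalteparin (15.29b).** There are four items: self-injection technique, a bleeding warning ("Warn patient of increased risk of bleeding, including life threatening hemorrhage"), liver function monitoring, and procedures ("Instruct patients that they need to notify their provider prior to any procedures, as their risk for bleeding is significantly increased"). None mentions aspirin, NSAIDs, antiplatelet drugs or a medication review.

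The drug-interaction paragraphs recognise the hazard for both drugs. For apixaban, 15.17 says: "Coadministration of antiplatelet agents, fibrinolytics, heparin, aspirin, and chronic NSAID use increases the risk of bleeding". For dalteparin, 15.27 says: "Dalteparin should be used with care in patients receiving oral anticoagulants, platelet inhibitors, and thrombolytic agents because of increased risk of bleeding". The dalteparin paragraph names platelet inhibitors but not aspirin or NSAIDs, and it asks no one to speak to the patient.

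**The concern.** Aspirin and NSAIDs raise the risk of the event that this trial counts. An instruction to counsel against them in one arm only is a co-intervention tied to allocation. Treatment is open-label (1.5), so staff know which list applies. The primary analysis (16.21) concentrates on bleeds during treatment or within 7 days of stopping, which is when the advice would act.

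If the text changes behaviour, it lowers bleeding on apixaban through co-medication and not through the study drug, in the direction of the hypothesis. Blinded adjudication (1.5) guards against biased classification. It cannot remove a real difference in bleeds.

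There are two smaller consequences for patients. Those on dalteparin may miss a precaution that 15.27 supports. Those on apixaban who need low-dose aspirin may be told to avoid it although 9.2 allows it.

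**Working it through.** **Comparing the texts.** 15.19b has three bleeding-related items. Two have a counterpart in 15.29b and one does not.

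| Item | Apixaban 15.19b | Dalteparin 15.29b |
|---|---|---|
| Bleeding warning | yes | yes |
| Tell the team or provider before procedures | yes | yes |
| Avoid aspirin/NSAIDs | yes | no |

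Pharmacology does not explain the gap. The CYP3A4/P-gp and herbal review is properly specific to apixaban and is not at issue, but the added bleeding risk with platelet inhibitors is stated for dalteparin too (15.27). The body text describes the written patient materials in appendix IX as covering symptoms of VTE recurrence (7.13) and injection technique (15.24). It mentions no co-medication advice there.

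**The plan's own figure.** Inputs from 16.1: hazard ratio (HR) 0.22, one-sided alpha 0.05, power 80%, 1:1 allocation. Schoenfeld's formula gives 4 × (1.645 + 0.842)² / (ln 0.22)² = 10.8, or 11 events, as 16.1 states. Expected bleeds in 300 patients are 150 × 6.0% + 150 × 1.4% = 9.0 + 2.1 = 11.1. The designed difference is 9.0 − 2.1 = 6.9 bleeds. Nothing in this point disputes these figures.

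**How large the effect could be.** The documents give neither usage rates nor a relative risk for users. The following are assumptions for illustration:

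- use on dalteparin, p_D = 20%
- use on apixaban, p_A = 20%, 15% or 10%
- relative risk of major bleeding in users, RR = 1.5 or 2.0
- the two study drugs are equally safe, with 9 bleeds per 150 dalteparin patients (6%)

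Formulas:

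- Spurious HR = [1 + p_A(RR − 1)] / [1 + p_D(RR − 1)]
- Expected apixaban bleeds = 9 × HR
- One-sided type I error = Φ(−1.645 − ln(HR) × √D / 2), with D = 11 (the trigger in 16.1) or D = 18 (300 × 6%, the expected number if both arms bleed at the control rate)

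| p_A vs p_D | RR | HR | Fewer apixaban bleeds | Type I error, D = 11 | Type I error, D = 18 |
|---|---|---|---|---|---|
| 20% vs 20% | 1.5 or 2.0 | 1.000 | 0 | 5.0% | 5.0% |
| 15% vs 20% | 1.5 | 0.977 | 0.20 | 5.4% | 5.5% |
| 15% vs 20% | 2.0 | 0.958 | 0.38 | 5.8% | 6.0% |
| 10% vs 20% | 1.5 | 0.955 | 0.41 | 5.8% | 6.1% |
| 10% vs 20% | 2.0 | 0.917 | 0.75 | 6.7% | 7.2% |

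As an example, the last row has HR = (1 + 0.10) / (1 + 0.20) = 0.917, apixaban bleeds 9 × 0.917 = 8.25, and type I error at 11 events Φ(−1.645 + 0.0870 × 3.317 / 2) = Φ(−1.50) = 6.7%.

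As a share of the designed log hazard ratio (ln 0.22 = −1.514), these effects run from 0.023 / 1.514 = 1.5% to 0.087 / 1.514 = 5.7%. The normal approximation is rough with 11 events, so the type I error figures indicate scale only.

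**The case against.** The strongest reply is that the operative rule already treats the arms alike. Section 9.2 discourages these drugs for everyone, caps aspirin and requires use to be recorded. Thienopyridines are barred in both arms (3.26, 9.3), and selected concomitant medication is collected at baseline and every 30 days (4.0). On this view 15.29b merely lacks one repeated line, and 15.27 supplies the caution. To *avoid* can be read as an ordinary way of discouraging that leaves the low-dose aspirin exception intact. The consent form, appendices and package inserts are not in the supplied text and may give both arms the same advice. The usage and relative-risk values are assumed, and the upper case needs one nursing sentence to halve use relative to a control arm already under 9.2.

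Most of this stands as a limit on size. The documents show a difference in instructions, not in use, and common advice elsewhere cannot be ruled out. It does not remove the point. Section 9.2 sets a rule but gives the counselling to no one; in the text available, only 15.19b assigns it, for one arm and in firmer words. Section 15.27 informs staff but does not ask them to tell the patient. Recording use lets a difference be seen afterwards but does not prevent it.

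**Conclusion.** The point holds as a minor one. The nursing instructions differ between arms on a recognised cause of bleeding, nothing in the drug information justifies the difference, and any effect would favour apixaban. Its size cannot be estimated from the documents. Under the assumed values the bias is below one bleed, with type I error at most 6.7% at 11 events and 7.2% at 18. It could not by itself produce the designed effect. If both arms receive the same advice through consent or appendix material, or if staff simply apply 9.2 to everyone, the effect may be nil. It is worth correcting because it bears on the primary endpoint and is very cheap to remove.

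**What to change.** Put one identical sentence in 15.19b and 15.29b, worded to agree with 9.2. For example: *Tell patients that aspirin and NSAIDs, including over-the-counter products, are discouraged during study treatment; ask about their use; keep any necessary aspirin to 100 mg daily or less; enter all use on the CRF.* Leave the CYP3A4/P-gp and herbal review in the apixaban section only.

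As an optional addition, report on-study aspirin and NSAID use by arm in a descriptive table, so that readers can see whether use differed.

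The cost is one sentence in each of two sections, a brief conversation with each dalteparin patient and, if wanted, one table from data already collected under 9.2 and at the 30-day visits. No visit, form, sample size, alpha level or analysis changes.

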15.2 Dalteparin (Fragmin®) Commercial supply

Package Insert is available on the ACCRU web site.

- 15.21 **Background:** Dalteparin is a low molecular weight heparin with antithrombotic properties. It acts by enhancing the inhibition of Factor Xa and thrombin by antithrombin. In humans, dalteparin potentiates preferentially the inhibition of coagulation Factor Xa, while only slightly affecting the activated partial thromboplastin time (APTT).

Dalteparin is used for the prevention of deep vein thrombosis (DVT) which may lead to pulmonary embolism, in patients requiring abdominal surgery who are at risk for thromboembolism complications (eg, patients >40 years of age, obesity, patients with malignancy, history of DVT or pulmonary embolism, and surgical procedures requiring general anesthesia and lasting >30 minutes); prevention of DVT in patients undergoing hip-replacement surgery; patients immobile during an acute illness; prevention of ischemic complications in patients with unstable angina or non-Q-wave myocardial infarction on concurrent aspirin therapy; in patients with cancer, extended treatment (6 months) of acute symptomatic venous thromboembolism (DVT and/or PE) to reduce the recurrence of venous thromboembolism.

- 15.22 **Formulation:** Dalteparin sodium injection (Fragmin®) is available as single dose prefilled syringes in the following sizes: 2,500 IU/0.2 mL, 5,000 IU/0.2 mL, 7,500 IU/0.3 mL, 12,500 IU/0.5 mL, 15,000 IU/0.6 mL, and 18,000 IU/0.72 mL. It is also available as a single-dose graduated syringe of 10,000 IU/1 mL, and is available as a multiple dose vial containing 95,000 IU/3.8 mL (25,000 IU/mL).

Each prefilled syringe also contains Water for Injection and sodium chloride, when required, to maintain physiologic ionic strength. The prefilled syringes are

preservative-free. Each multiple-dose vial also contains Water for Injection and 14 mg of benzyl alcohol per mL as a preservative. The pH of both formulations is 5.0 to 7.5

- 15.23 **Preparation and storage:** Store at controlled room temperature 20° to 25°C (68° to 77°F)Store at 20°C to 25°C (68°F-77°F) [see USP]. Please see package insert.
- 15.24 **Administration:** Dalteparin will be given 200 IU/kg/day subcutaneously. The dosage will be calculated on the patient's current weight in kilograms, rounded to the nearest whole kilogram. The syringe dose will be chosen based on the weight adjusted calculation (see table 7.11). . The patient will be taught by on site nursing staff how to "waste" from each syringe such that the appropriate weight adjusted dose is delivered. After the first month, dalteparin will be given 150 IU/kg/day subcutaneously. Dalteparin will be dispensed in one month supply aliquots to the patient. Dalteparin will be stored according to the package insert. Patient instructions on proper subcutaneous injection techniques are included in appendix IX.
- 15.25 **Appearance:** Colorless solution in single-dose, prefilled syringes preassembled with a needle guard device. Each syringe contains 2,500, 5,000, 7,500, 10,000, 12,500, 15,000 or 18,000 anti-Factor Xa international units (IU).
- 15.26 **Pharmacokinetic information:**
- a) Onset of action - Anti-Xa activity: Within 1-2 hours
 - b) Duration - >12 hours
 - c) Distribution - Vd: 40-60 mL/kg
 - d) Protein binding - Low affinity for plasma proteins
 - e) Bioavailability - SubQ: 81% to 93%
 - f) Half-life elimination (route dependent) - Anti-Xa activity: 2-5 hours; prolonged in chronic renal insufficiency: 3.7-7.7 hours (following a single 5000 unit dose)
 - g) Time to peak, serum - Anti-Xa activity: ~4 hours
 - h) Excretion - Primarily renal
- 15.27 **Potential drug interactions:** Dalteparin should be used with care in patients receiving oral anticoagulants, platelet inhibitors, and thrombolytic agents because of increased risk of bleeding.
- Please consult current drug reference sources for a complete list of potential drug interactions.
- 15.28 **Known potential toxicities:** As with all anticoagulants, bleeding is the major adverse effect of dalteparin. Hemorrhage may occur at virtually any site. Risk is dependent on multiple variables. Please consult the package insert for the most current and complete information.

Adverse effects by frequency:

>10%:

Hematologic & oncologic: Hemorrhage (3% to 14%), thrombocytopenia (including heparin-induced thrombocytopenia, <1%; cancer clinical

trials: ~11%)

1% to 10%:

Hematologic & oncologic: Major hemorrhage ($\leq 6\%$), wound hematoma (3%)

Hepatic: Increased serum ALT ($>3 \times \text{ULN}$: 4% to 10%), increased serum AST ($>3 \times \text{ULN}$: 5% to 9%)

Local: Pain at injection site ($\leq 12\%$), hematoma at injection site ($\leq 7\%$)

$<1\%$ (Limited to important or life-threatening):

Alopecia, anaphylactoid reaction, gastrointestinal hemorrhage, hemoptysis, hypersensitivity reaction (fever, pruritus, rash, injections site reaction, bullous eruption), postoperative wound bleeding, skin necrosis, subdural hematoma, thrombosis (associated with heparin-induced thrombocytopenia). Spinal or epidural hematomas can occur following neuraxial anesthesia or spinal puncture, resulting in paralysis.

- 15.29a **Drug procurement:** Pfizer will supply the drug to Biologics, Inc. Each participating ACCRU treating location will order the drug from Biologics, Inc. Fax the Drug Order Request Form (found in the forms packet) to:
Biologics, Inc.
Attn. Clinical Research Services
Fax: [REDACTED]

Each participating ACCRU treating location will be responsible for monitoring the supply of dalteparin and will use the Drug Order Request Form to order additional supplies as needed.

Outdated or remaining drug is to be destroyed on-site as per procedures in place at each institution.

15.29b Nursing guidelines:

- Instruct patients on self-injection technique.
- Warn patient of increased risk of bleeding, including life threatening hemorrhage. Patients should report excessive bruising and/or bleeding to the study team.
- Monitor LFT's and alert study team to changes in values.
- Instruct patients that they need to notify their provider prior to any procedures, as their risk for bleeding is significantly increased.

